2.2 PRIMARY ENDPOINT(S) ANALYSIS

2.2.1 Definition of endpoint(s)

The primary endpoint is the percentage of biologic and small molecule immunosuppressive-naïve participants achieving HiSCR50 at Week 16. It is defined as $\geq 50\%$ reduction from Baseline in the total abscess and inflammatory nodule (AN) count, with no increase from Baseline in abscess or draining tunnel count.

2.2.2 Main analytical approach

The primary endpoint will be analyzed with the primary estimand defined according to the following attributes:

- Endpoint: Percentage of participants achieving HiSCR50 at Week 16.
- Treatment condition: SAR442970 will be compared to Placebo.
- Analysis population: Biologic and small molecule immunosuppressive-naïve population of Period A.
- Intercurrent events (IE):

The following intercurrent events will be handled with the composite variable strategy; participants will be considered as non-responders after such IE:

- Starting or increase in dose of oral antibiotic therapy for HS prior to Week 16
- Starting selected prohibited medications. Participants that receive the selected treatment listed in [Table 5](#) will be reviewed in a blinded fashion to make sure the medication was used due for HS treatment failure and not an unrelated condition.
- Discontinuation of study intervention due to lack of efficacy

The following IEs will be handled with the treatment policy strategy (without IEs that need to be handled with composite variable strategy). Data collected after starting such IE will be included:

- Starting other prohibited medications

- Discontinuation of study intervention due to reasons other than lack of efficacy
- Population-level summary: A Bayesian logistic regression model including intervention group and stratified by baseline Hurley Stage will be used with an informative prior on the placebo response rate based on the historical studies available. Participant with missing data will be imputed as non-responders. Descriptive statistics will be presented by treatment group.

Table 5 - Selected prohibited and/or rescue medications and procedures impact on efficacy

Endpoints	Intervention (Intercurrent Event)	Intervention in the main statistical analysis (Yes/No) ^a / Selection criteria
Percentage of participants achieving HiSCR50 at Week 16 and other endpoints derived from HS clinical parameters (eg, HiSCR75, HiSCR90, IHS4, flares, DLQI, HiSQOL)	Immunosuppressive or immunomodulatory therapy Examples: natalizumab, rituximab, adalimumab, certolizumab pegol, etanercept, golimumab, infliximab, anakinra, canakinumab, bermekimab, ustekinumab, guselkumab, secukinumab, JAK inhibitors (e.g., abrocitinib, baricitinib, filgotinib, pacritinib, upadacitinib), or TYK inhibitors (e.g., brepocitinib deucravacitinib, ropsacitinib), or apremilast, corticosteroids, methotrexate, cyclosporine, retinoids, acitretin/etretinate, non-contraceptive hormonal therapy, zinc gluconate, intramuscular gamma globulin, colchicine, fumaric acid esters, or metformin (except for continuous treatment of pre-existing diabetes), or other systemic therapies that can also be used to treat HS.	No
	Antibiotic therapy Antibiotic therapy (topical and/or systemic [oral or IV]) for HS-related infection other than doxycycline or minocycline	Yes (CDGsn00892)
	Doxycycline or minocycline: Increase from stable dose established 28 days prior to baseline; or increase dose regimen greater than 100 mg PO BID for doxycycline or minocycline	Yes (CDGsn00892)
	Corticosteroid therapy Intralesional corticosteroids	No
	Corticosteroids for HS with systemic potential (e.g., injectable or high dose intralesional corticosteroids)	Yes (CDGsn00010)
Pain endpoints (HS skin pain NRS, PP NRS)	Analgesic therapy within 5 days preceding Week 16 visit Opioid analgesics and Non-opioid analgesics (e.g., antiepileptics (e.g., gabapentin), tricyclics (e.g., nortriptyline), or selective serotonin norepinephrine reuptake inhibitors (e.g., duloxetine, venlafaxine) other than ibuprofen or acetaminophen	Yes (CDGsn00195; CDGsn00229 ;CDGsn01761; CDGsn00009; CDGsn01793)
	Corticosteroid therapy Intralesional corticosteroids for HS	Yes (CDGsn00010)
	Incision and drainage procedure for HS	Yes (CMQ40194)

a When yes, if confirmed through blinded medical review the estimand for the intercurrent event handling strategy will be as follows: hypothetical for continuous endpoints, and composite for responder and time-to-event endpoints. When no, a treatment policy strategy will be applied.

Bayesian modeling

The following Bayesian logistic regression for the mean binary response will be used:

$$\ln\left(\frac{E(y)}{1-E(y)}\right) = \text{logit}(E(y)) = \beta_{PBO}X_{PBO} + \beta_{TRT}X_{TRT} + \beta_{HS2}X_{HS2} + \beta_{HS3}X_{HS3}$$

Where X_{PBO}, X_{TRT} are dummy variables taking the value 1 or 0 according to whether or not each of participant is in the placebo or SAR442970 treatment group respectively, X_{HS2}, X_{HS3} are dummy variables taking the value 1 or 0 according to whether or not each of participant is in the Hurley stage II or III groups respectively.

For parameter estimation, the following constraint will be used:

$$\beta_{HS2} = -\beta_{HS3}$$

Giving the model:

$$\ln\left(\frac{E(y)}{1-E(y)}\right) = \text{logit}(E(y)) = \beta_{PBO}X_{PBO} + \beta_{TRT}X_{TRT} + \beta_{HS2}(X_{HS2} - X_{HS3})$$

so that the influence of Baseline Hurley Stage on the model estimated treatment group mean responses are more evident.

The expectations of the prior distributions for the biologic and small molecule immunosuppressive-naïve population in the placebo group response rates will be set to match the observed treatment group response rates in the available historical studies. An informative prior distribution for the HiSCR50 rate has been chosen as a beta distribution with parameter (2.1; 4.9) which have expectations equal to 30% for the placebo group to match the observed treatment group response rates of the historical studies. A vague uninformative prior (a prior with a large variance) will be used for the biologic and small molecule immunosuppressive-naïve population in the treatment group because there are few to no prior data published on SAR442970 in HS).

IF p_{TRT}, p_{PBO} denote the probability of response in the treatment group and placebo group respectively, to map the probability scale priors for the group response rates and the logit scale treatment group we will use the following equations :

$$p_{PBO} = \text{logit}^{-1}(\beta_{PBO})$$

$$p_{TRT} = \text{logit}^{-1}(\beta_{TRT})$$

Accordingly, the priors to be used are :

$$\beta_{PBO} \sim \beta (2.1; 4.9)$$

$$\beta_{TRT} \sim N (0; 10000)$$

$$\beta_{HS2} \sim N (0; 10000)$$

The model equation will be updated to parameterize β_{PBO} as the model intercept with the active treatment being additive effects (on the logit scale). We note that model (2) can be re-parameterized as follows:

$$\beta_{PBO} = \gamma_{PBO}$$

$$\beta_{TRT} = \gamma_{TRT} + \gamma_{PBO}$$

$$\beta_{HS2} = \gamma_{HS2}$$

Giving the model:

$$\ln\left(\frac{E(y)}{1 - E(y)}\right) = \text{logit}(E(y)) = \gamma_{PBO} + \gamma_{TRT}X_{TRT} + \gamma_{HS2}(X_{HS2} - X_{HS3})$$

Presentation of results from the primary analysis

The priors and observed data will be combined and used to derive posterior distributions for the response rates in each treatment arm. The posterior distributions will be summarized using means, medians, SDs and the 80% and 90% credible intervals.

The posterior probability that the difference in response rates between placebo and SAR442970 groups is greater than zero (i.e., SAR442970 demonstrates a greater response compared with placebo) will also be presented.

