- v* All eligible participants will be treated for 28 weeks, receiving a SC administration of IMP or placebo every 2 weeks for the first 14 weeks based on randomization, and then starting at Week 16 (Visit 10) all participants will receive IMP every 2 weeks until the last dose is administered at Week 26 (Visit 15).
- w* Per Investigator discretion, participants may resume treatment for HS as needed (including, but not limited to oral and topical antibiotics, corticosteroids, opioid and non-opioid analgesics, spironolactone, finasteride, or metformin). Participants may also receive unlimited lesion intervention as needed per Investigator discretion.
- x* Vital signs, including body temperature (°C), heart rate (beats per minute), respiratory rate (breaths per minute), and systolic and diastolic blood pressure (mm Hg), will be measured at all visits detailed in the flowchart.
- y* Physical examination will include examination of skin, nasal cavities, eyes, ears, cardiovascular, respiratory, gastrointestinal, neurological, lymphatic, and musculoskeletal systems. A brief symptom-directed physical examination should be performed at other visits if, in the opinion of the Investigator, it is warranted by the participant's AE status or on review of symptoms and will include, at a minimum, assessments of the skin, cardiovascular system, and abdomen (liver and spleen). Height will be measured and recorded at the Screening Visit. Weight will also be measured and recorded at the Screening, Baseline, Week 16, and EOS Visit.
- z* For fasting lipid panel, participant must be fasting for 8 hours prior to laboratory testing (may consume water). If unable to fast, participant may consume a light meal. Labs drawn during non-fasting laboratory testing will include hematology and clinical chemistry only. For laboratory testing please see [Table 12](#).
- aa* Only for WOCBP: serum pregnancy test at Screening (Visit 1) and urine pregnancy tests at every visit from Baseline (Visit 2) to EOS (Visit 17). A negative result must be obtained at Screening (Visit 1) and at Baseline (Visit 2) prior to randomization. In case of positive urine test, the study treatment will be withheld and a serum pregnancy test to confirm the pregnancy should be performed as soon as possible. Pregnancy will lead to definitive treatment discontinuation in all cases.

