Secondary endpoint- Skin pain	
Percentage of participants achieving at least 30% reduction and at least 1 unit reduction from Baseline in weekly average of daily HS Skin Pain NRS at Week 16 among participants with Baseline NRS = 3 (HS-Skin Pain NRS is based on worst skin pain in a 24-hour recall period [daily assessment is averaged over 7-day period])
	Biologic and small molecule immunosuppressive-naïve population of Period A	
The following IEs will be handled with the composite variable strategy; participants will be considered as non-responders after such IE.
 
 Using analgesic therapy within 5 days of Week 16 will be considered as non-responders Discontinuation of study intervention due to lack of efficacy. 
The following IE will be handled with the treatment policy strategy (without IEs that need to be handled with
	
CMH method including treatment group and stratified by baseline Hurley Stage.
 
The difference of the response rates between SAR442970 and placebo and the 80% and 90% confidence intervals will be derived.
 
Participants with missing data will be imputed as non-responder.

Endpoint Category	Estimands			
	Endpoint(s)	Population	Intercurrent event(s) handling strategy	Population-level summary and missing data handling
			
composite variable strategy). Data collected after starting such IE will be included.
 
• Discontinuation of study intervention due to reasons other than lack of efficacy.	

a The list of medications will be selected by blinded medical review prior to database lock. Participants that receive the selected treatment will also be reviewed in a blinded fashion to make sure the medication was used due for HS treatment failure and not an unrelated condition.

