The percentage of participants achieving at least 30% reduction and at least 1 unit reduction from Baseline in weekly average of daily HS Skin Pain NRS at Week 16 among participants with Baseline NRS ≥ 3 (HS-Skin Pain NRS is based on worst skin pain in a 24-hour recall period [daily assessment is averaged over 7-day period]) will be analyzed. Participants must have a minimum of 4 diary entries within the 7-day period prior to Week 16 to calculate the week's average. Those who don't meet this requirement will have missing data for that week.

The estimand for skin pain endpoint will be used and participants with missing data will be imputed as non-responders. The following IEs will be handled with the composite variable strategy; participants will be considered as non-responders after such IE.

- Using analgesic therapy within 5 days of Week 16 will be considered as non-responders.
- Starting selected prohibited medications. Participants that receive the selected treatment listed in Table 5 will be reviewed in a blinded fashion to make sure the medication was used due for HS treatment failure and not an unrelated condition.
- Discontinuation of study intervention due to lack of efficacy.

The following IE will be handled with the treatment policy strategy (without IEs that need to be handled with composite variable strategy). Data collected after starting such IE will be included.

- Discontinuation of study intervention due to reasons other than lack of efficacy.

Participants with missing data will be imputed as non-responders.

An estimate of the treatment difference (SAR442970 versus placebo) will be obtained using CMH method, stratified by baseline Hurley stage. The estimated treatment difference will be reported along with the 80% and 90% confidence intervals.

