Week 4	29	22 - 42	22 - 42		22 - 42
Week 6	43				
Week 8	57	43 - 70	43 - 70		43 - 70
Week 10	71				
Week 12	85	71 - 98	71 - 98		71 - 98
Week 14	99				
Week 16	113	99 - D ^b	99 - D ^b		99 - D ^b
Period B					
Week 18	15				
Week 20	29	2 - 42	2 - 42		2 - 42
Week 22	43				
Week 24	57	43 - 70	43 - 70		43 - 70
Week 26	71				
Week 28	85	>70	>70		>70

^a Day 1 in Period A is the day of the first blinded IMP administration (or the day of randomization for participant not exposed). Day 1 in Period B is the day of the first open-label IMP administration.

^b Last window in Period A is the 1st dose of open-label IMP administration.

Table 14 - Analysis window definition for daily questionnaires

Analysis visit	Targeted study day ^a	Time windows		
		Daily Diary HS-Skin Pain NRS	Daily Diary PP-NRS	Daily diary analgesic use
Period A				
Screening	-28 to -7	<-7	<-7	<-7
Baseline	1	-7 - <1	-7 - <1	-7 - <1
Week 2	15	8 - 14	8 - 14	8 - 14
Week 4	29	22 - 28	22 - 28	22 - 28
Week 6	43	36 - 42	36 - 42	36 - 42
Week 8	57	50 - 56	50 - 56	50 - 56
Week 10	71	64 - 70	64 - 70	64 - 70
Week 12	85	78 - 84	78 - 84	78 - 84
Week 14	99	92 - 98	92 - 98	92 - 98
Week 16	113	106 - D ^b	106 - D ^b	106 - D ^b
Period B				
Week 18	15	8 - 14	8 - 14	8 - 14
Week 20	29	22 - 28	22 - 28	22 - 28
Week 22	43	36 - 42	36 - 42	36 - 42
Week 24	57	50 - 56	50 - 56	50 - 56
Week 26	71	64 - 70	64 - 70	64 - 70
Week 28	85	78 - 84	78 - 84	78 - 84

a Day 1 in Period A is the day of the first blinded IMP administration (or the day of randomization for participant not exposed). Day 1 in Period B is the day of the first open-label IMP administration.

b D = minimum (Day 112, the day prior to the first open-label IMP)

Table 15 - Analysis windows for pharmacokinetics/pharmacodynamics variables

Analysis visit	Targeted study day ^a	Time windows				
		ADA	Blood biomarkers	PK	PD Biomarker	Skin Biopsy
Period A						
Screening	-28 to -14	<-14	<-14		<-14	
Baseline	1	-14 - 1	-14 - 1	≤1	-14 - 1	≤1
Week 2	15	2 - 21	2 - 21		2 - 21	
Week 4	29	22 - 42	22 - 42	2 - 49	22 - 42	
Week 6	43					
Week 8	57	43 - 70	43 - 70	50 - 63	43 - 70	
Week 10	71			64 - 77		
Week 12	85	71 - 98	71 - 98	78 - 98	71 - 98	
Week 14	99					
Week 16	113	99 - D ^b	> 1			
Period B						
Week 18	15			2 - 21		
Week 20	29	2 - 42	2 - 42	22 - 70	2 - 42	
Week 22	43					
Week 24	57	43 - 70	43 - 70		43 - 70	
Week 26	71					
Week 28	85	71 - 112	> 70	71 - 112	71 - 112	
Week 36	141	> 112		> 112	> 112	

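### The Week 16 skin-pain average includes diary days that the 5-day analgesic check does not cover: 2 of 7 at an on-time visit

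*SAP*

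**What the plan says.** The endpoint (SAP Section 2.3.3) is "at least 30% reduction and at least 1 unit reduction from Baseline in weekly average of daily HS Skin Pain NRS at Week 16". It is restricted to those whose baseline score is 3 or more. The "daily assessment is averaged over 7-day period", and a participant needs "a minimum of 4 diary entries within the 7-day period prior to Week 16"; with fewer, the week is missing and imputed as non-response.

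SAP Section 4.4, Table 14 sets the scored days as Day 106 to D, with "D = minimum (Day 112, the day prior to the first open-label IMP" in footnote b. The same table gives the daily analgesic diary the identical Week 16 window.

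The analgesic intercurrent event is defined with two anchors:

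- Table 5 (Section 2.2.2), in the row shared by HS Skin Pain NRS and PP-NRS: "Analgesic therapy within 5 days preceding Week 16 visit". This row counts opioids and non-opioids but exempts ibuprofen and acetaminophen.
- Table 3 (Section 1.2.1), repeated in Section 2.3.3: "Using analgesic therapy within 5 days of Week 16 will be considered as non-responders". No drug is exempted here.

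The Protocol schedule puts the Week 16 visit on Day 113, plus or minus 3 days. Open-label dosing begins at that visit: "starting at Week 16 (Visit 10) all participants will receive IMP every 2 weeks".

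**The concern.** The composite strategy is there so that a pain score lowered by an analgesic does not count as response. That works only if every day entering the average is also a day on which analgesic use is checked. Here the two windows differ in length (up to 7 days against 5), and under Table 5 they also differ in anchor (study days against the actual visit).

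A counted analgesic taken on an early scored day could therefore lower the mean without triggering the event. For late visits the reverse is possible: the look-back extends past the last scored day, so an analgesic that cannot have affected the score might make the participant a non-responder. At stake is the classification of individual participants on the endpoint that carries the secondary pain objective, and on PP-NRS.

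**Working it through.** **Inputs.** Scored window: Day 106 to min(112, day before first open-label dose), from Table 14. Look-back: 5 days before the visit, from Table 5. Visit day v: 110 to 116, from the Protocol schedule. First open-label dose taken to be given at the Week 16 visit.

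**The plan's own figure.** 112 − 106 + 1 = 7 days, which matches the stated 7-day averaging period.

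**Formulas.** Scored days = 106 to min(112, v − 1). Checked days = v − 5 to v − 1. Unchecked = scored days that are not checked. Late = checked days after Day 112.

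| Visit day | Scored | Checked | Unchecked scored days | Late checked days |
|---|---|---|---|---|
| 110 | 106–109 (4) | 105–109 | 0 | 0 |
| 111 | 106–110 (5) | 106–110 | 0 | 0 |
| 112 | 106–111 (6) | 107–111 | 1 (106) | 0 |
| 113 | 106–112 (7) | 108–112 | 2 (106–107) | 0 |
| 114 | 106–112 (7) | 109–113 | 3 (106–108) | 1 |
| 115 | 106–112 (7) | 110–114 | 4 (106–109) | 2 |
| 116 | 106–112 (7) | 111–115 | 5 (106–110) | 3 |

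On Day 113 the unchecked share is 2/7 = 29%. On Day 116 it is 5/7 = 71%. For visits on Days 115 and 116, the 4-entry minimum can be met by unchecked days alone.

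**Other anchor.** If the 5 days run back from nominal Day 113 (Days 108–112), the unchecked days are 106 and 107, so the count is 2 at an on-time or later visit and no checked day falls after Day 112.

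**Can it change a result?** This is an illustration; the scores are assumed. With a baseline of 6.0, response needs a mean of at most 0.7 × 6.0 = 4.2 (the 1-unit condition, 5.0, is weaker). Unmedicated scores of 5 on all days give 5.0, a reduction of 1/6 = 17%, which is non-response. For an on-time visit with a counted analgesic on Days 106–107 only:

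- score 1 on those two days: (2 × 1 + 5 × 5)/7 = 3.86, a responder;
- score 2 on those two days: (2 × 2 + 5 × 5)/7 = 4.14, still a responder.

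More generally, a drop of s points on k of 7 days lowers the mean by k × s/7. For s from 2 to 4 this is 0.57 to 1.14 with k = 2, and 1.43 to 2.86 with k = 5.

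**Does another rule close the gap?** Section 2.3.3 also lists the start of selected prohibited medications as a composite event, but it refers to Table 5, whose analgesic row carries the 5-day limit. Table 3's pain row does not list that event. Blinded medical review confirms events that Table 5 already counts; nothing says it lengthens the window. Protocol Section 6.9.1 keeps users of prohibited analgesics on IMP. Stopping IMP for a reason other than lack of efficacy is handled by treatment policy, so the scores would still count.

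**The case against.** Four points can fairly be made.

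- **The range.** A reader might infer that 2 to 5 of 7 scored days are always unchecked. That holds only for visits on Days 113 to 116 under the Table 5 anchor. For Days 110 to 112 the diary window shortens to 4 to 6 days and the gap is 0, 0 and 1. Table 3 and Section 2.3.3, which state the estimand, do not mention the visit; read on nominal Day 113, they give 2 days at an on-time or later visit. This stands.
- **Errors in both directions.** A reader might infer that false non-responders are certain. They arise only for visits on Days 114 to 116 under the Table 5 anchor, and only if the check is not confined to the analgesic-diary window in Table 14, which closes at D. Table 5 lists drug-group codes, which suggests coded medications, but the SAP does not name the source. This stands: that direction is possible, not shown.
- **Few participants.** Table 5 exempts ibuprofen and acetaminophen, and most other analgesics are restricted in Period A, apart from tramadol rescue in Australia and stable non-opioids for non-HS pain. Stable use that runs into the last 5 days is caught at an on-time visit. The gap needs use on the early days and none in the checked days. This stands, but the wider wording in Table 3 and Section 2.3.3 would bring in ibuprofen and acetaminophen, which all participants may take.
- **The illustration is selective.** It assumes relief of 3 to 4 points on exactly two days. That is fair; it shows that a change of status is possible, not that it is common.

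None of this removes the two unchecked days at an on-time visit.

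**Conclusion.** The scored and checked windows do not match. At an on-time visit 2 of 7 scored days are unchecked on either anchor. Across all permitted visit days the count is 0 to 5 under Table 5. These counts assume that the first open-label dose is given at the Week 16 visit and that the look-back is the 5 days before it.

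A reader might go on to infer that false responders would gather on placebo and shrink the treatment difference. The documents give no analgesic usage rate by arm, so neither the direction nor the size of any bias can be stated.

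This is a wording defect in one secondary endpoint and PP-NRS, in a proof-of-concept study. It does not touch HiSCR50. It merits correction because the rule falls short of its own purpose and the data for a matched check are already planned.

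**What to change.** In Table 3, Section 2.3.3 and Table 5, define the event as use of a counted analgesic on any day in the Table 14 Week 16 window (Day 106 to D), whether or not a pain score was entered that day. Use the same definition for PP-NRS, and name the data source for the check.

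Two simpler edits fall short. Lengthening the look-back to 7 days before the actual visit still leaves 1, 2 and 3 unchecked days for visits on Days 114, 115 and 116. Checking only days with an entered score would drop checks the plan now makes, since 3 of the 7 days may have no entry.

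The matched window gives 0 unchecked scored days for every visit day. It stops checking Day 105 for a Day 110 visit and Days 113 to 115 for late visits; none of these days enters the average. While these lines are open, the ibuprofen and acetaminophen exemption in Table 5 should be reconciled with the unrestricted wording in Table 3 and Section 2.3.3.

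The cost is SAP wording in three places and no new data. The downside is that a few more participants may be scored as non-responders.

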1.1 STUDY DESIGN

This is a multinational, randomized, placebo-controlled, double-blind, Phase 2a proof-of-concept study. The purpose of this study is to evaluate the efficacy, safety, PK, biological effects of SAR442970 compare with placebo in adult participants with moderate to severe hidradenitis suppurativa (HS).

The study is composed of 3 parts: a double-blind, placebo-controlled period (Period A), followed by an open-label period (Period B), and then a safety Follow-up Period (Period C). After a screening period of 2 to 4 weeks, participants will receive SAR442970 150 mg or matching placebo Q2W at the Week 0 visit up to the Week 14 visit as part of Period A. Beginning at the Week 16 visit, all participants will receive SAR442970 150 mg Q2W up to the visit prior to the individual participant's end of treatment (EOT) visit as part of Period B. Period C will commence with the End of Treatment (EOT) visit and conclude with the End of Study (EOS) visit. For participants in the US, response will be assessed at the Week 20 visit (see definition of response in [Section 2.2.1](#)). Responders at Week 20 will continue in Period B to complete the 12-week open-label period. Non-responders at Week 20 will move directly to the safety follow-up period (Period C) with the Week 20 visit serving as their EOT visit.

Approximately 84 participants will be randomized in a 2:1 ratio to SAR442970 150 mg Q2W or matching placebo. Randomization will be stratified by HS treatment history (biologic and small molecule immunosuppressive-naïve or TNF-experienced) and Hurley stage (II or III). The recruitment target is approximatively 66 biologic and small molecule immunosuppressive-naïve and approximatively 18 TNF-experienced. Within the biologic and small molecule immunosuppressive-naïve subgroup, the number of participants with Hurley Stage III is not to exceed more than 50%. Within the biologic and small molecule TNF-experienced subgroup, the number of participants with Hurley Stage III is not to exceed more than 50%.

The primary analysis population is the biologic and small molecule immunosuppressive-naïve subgroup. Efficacy objectives and endpoints will be evaluated in an exploratory manner in the TNF-experienced subgroup.

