1.2.1 Estimands

Primary estimand defined for main endpoints are summarized [Table 3](#) below. More details are provided in [Section 2](#). Additional secondary objectives/endpoints are not included in this table but would be handled with a similar strategy as the endpoint type (i.e., continuous, proportion, or time-to-event). For all these estimands, the comparison of interest will be the comparison of SAR442970 vs. placebo.

Table 3 - Summary of estimands for the primary and selected secondary endpoints

Endpoint Category	Estimands			
	Endpoint(s)	Population	Intercurrent event(s) handling strategy	Population-level summary and missing data handling
Primary objective: To evaluate the efficacy of SAR442970 during the double-blind, placebo-controlled period in the primary analysis population of the biologic and small molecule immunosuppressive-naïve subgroup participants with moderate to severe HS.				
Primary endpoint-Proportion	Percentage of participants achieving HiSCR50 at Week 16	Biologic and small molecule immunosuppressive-naïve population of Period A	
The following intercurrent events (IEs) will be handled with the composite variable strategy; participants will be considered as non-responders after such IE.
 
 Starting or increase in dose of oral antibiotic therapy for HS prior to Week 16. Starting selected prohibited medications^a. Discontinuation of study intervention due to lack of efficacy. 
The following IEs will be handled with the treatment policy strategy (without IE that need to be handled with composite variable strategy). Data collected after starting such IE will be included.
 
 Starting other prohibited medications. Discontinuation of study intervention due to reasons other than lack of efficacy. 	
The statistical analysis will be conducted using a Bayesian logistic regression model that includes the treatment group and stratified by baseline Hurley Stage. An informative prior on the placebo response rate will be used, based on the available historical studies.
 
The difference of response rates between SAR442970 and placebo along with the 80% and the 90% credible intervals will be derived.
 
Missing data will be imputed as non-responder.

Secondary objective: To evaluate the efficacy and safety of SAR442970 in the biologic and small molecule immunosuppressive-naïve subgroup of participants with HS.				

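### The SAP's only definition of an arm response rate is a logit midpoint between Hurley II and III, not the percentage of participants: arm rates could be several points off, while the treatment difference barely moves

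*SAP*

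**What the plan says.** The target in SAP 2.2.2 is "Endpoint: Percentage of participants achieving HiSCR50 at Week 16". The model there has one log-odds coefficient per arm (b_PBO, b_TRT) and one Hurley coefficient, b_HS2, multiplying a contrast that is +1 for Stage II and -1 for Stage III. The Stage III effect is constrained to be minus the Stage II effect, and there is no treatment-by-Hurley term.

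To link the priors on the rate scale to these coefficients, the SAP says that p_TRT and p_PBO "denote the probability of response in the treatment group and placebo group respectively" and sets p_PBO = logit⁻¹(b_PBO) and p_TRT = logit⁻¹(b_TRT). The placebo prior, Beta(2.1; 4.9) with mean 30%, was chosen to match historical placebo rates.

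The results paragraph then says that priors and data are "used to derive posterior distributions for the response rates in each treatment arm", summarised by means, medians, SDs and credible intervals. SAP Table 3 adds: "The difference of response rates between SAR442970 and placebo along with the 80% and the 90% credible intervals will be derived". The readable text nowhere describes averaging over the Hurley mix. On that mix, SAP 1.1 says only that in the naive subgroup "the number of participants with Hurley Stage III is not to exceed more than 50" per cent.

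**The concern.** Every participant has a Hurley contrast of +1 or -1. An arm coefficient taken alone describes a contrast of 0, which belongs to nobody. Its inverse logit is therefore not the percentage of participants responding unless Hurley stage has no effect. A programmer who follows the only formula given would report the midpoint as the arm's response rate.

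Two things are at stake. First, the arm-level posterior rates are a planned primary output. SAP 2.2.3 sets them beside arm rates from a Cochran-Mantel-Haenszel (CMH) analysis, partly to show how far the prior drives the result. A gap created by the coding could be read there as prior influence. Second, the historical 30% is attached to the same midpoint, although historical placebo rates describe mixtures of stages.

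**Working it through.** **Inputs.** 66 naive participants (Protocol 9.5); 2:1 allocation, so 44 and 22 (SAP 1.1); Beta(2.1; 4.9) and the model (SAP 2.2.2); Stage III at most 50% (SAP 1.1). Assumed, because the documents do not give them: true rates 30% placebo and 55% active, Stage III share s from 20% to 50%, and Hurley odds ratio (II versus III) from 1 to 3. The SAP prints the beta prior against b_PBO. A prior for a rate belongs on the rate, so it is placed on p_PBO here.

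**1. The plan's own figures.** Prior mean 2.1/(2.1 + 4.9) = 0.30; prior weight 2.1 + 4.9 = 7 participants. With independent beta posteriors, 44 versus 22, placebo at 30% and active rates from 40% to 70%, the 80% half-width for the difference is 0.138 to 0.144. This agrees with the stated value of less than 0.145. That check uses crude arm rates without Hurley stage.

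**2. Midpoint against percentage.** Let h = ln(OR)/2. The percentage responding in an arm is (1-s)·logit⁻¹(b+h) + s·logit⁻¹(b-h). The SAP's p is logit⁻¹(b). Take s = 0.30 and OR = 2, so h = 0.347:

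- Placebo: b = -1.007 gives 34.1% in Stage II and 20.5% in Stage III, and 0.70 × 34.1 + 0.30 × 20.5 = 30.0%. But logit⁻¹(-1.007) = 26.8%.
- Active: b = 0.065 gives 60.1% and 43.0%, and 0.70 × 60.1 + 0.30 × 43.0 = 55.0%. But logit⁻¹(0.065) = 51.6%.

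Both arms are low by just over 3 points, and the difference is 24.8 instead of 25.0.

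**3. Posterior means.** The SAP model was fitted on a grid to expected counts. Gaps are midpoint minus Hurley-averaged rate, in points (placebo / active / difference):

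| Stage III share | OR 2 | OR 3 |
|---|---|---|
| 20% | -4.6 / -5.2 / -0.6 | -7.3 / -8.3 / -1.0 |
| 30% | -3.5 / -3.4 / 0.0 | -5.6 / -5.5 / +0.1 |
| 40% | -2.2 / -1.6 / +0.6 | -3.7 / -2.5 / +1.2 |
| 50% | -0.8 / +0.2 / +1.0 | -1.5 / +0.5 / +2.0 |

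With OR = 1 the true gap is zero and the posterior gaps are at most 0.3 point. At s = 0.30 and OR = 2 the midpoint placebo mean is 27.4%, although the data and the prior mean are both 30%. The prior cannot explain that shortfall.

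**4. P(difference > 0).** With no interaction, the Hurley-averaged active rate exceeds the placebo rate exactly when b_TRT > b_PBO, draw by draw. The probability is the same under both definitions (0.9824 at s = 0.30, OR = 2).

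**5. Moving the prior.** Steps 3 and 4 leave the prior on the midpoint. Take a deliberately strong case: Stage II 22/34 versus 7/17, Stage III 2/10 versus 0/5. The observed rates are 24/44 = 54.5% and 7/22 = 31.8%, and the active-arm Hurley odds ratio is (22/12)/(2/8) = 7.3.

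| Prior on | Rate reported | Active | Placebo | Difference | P(difference > 0) |
|---|---|---|---|---|---|
| midpoint | midpoint | 38.6% | 20.3% | 18.3 | 0.958 |
| midpoint | Hurley-averaged | 54.5% | 34.9% | 19.6 | 0.958 |
| trial's Hurley mix | Hurley-averaged | 54.5% | 32.5% | 22.1 | 0.977 |

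The last row centres the Hurley term at its observed mean, which places the prior at the trial's mix on the logit scale. Where the prior is attached can therefore matter more than which rate is reported.

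**The case against.** The strongest reply is that the mapping exists to set priors, and that the SAP never says in so many words that logit⁻¹ of the coefficient is the reported rate. That is fair, and a reader should not infer an explicit statement. But if another quantity is meant, its formula is absent from the readable text.

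A reader might also infer that the treatment comparison is wrong or will disagree with CMH. The documents do not support that. Take Stage II 20/30 versus 6/15 and Stage III 5/14 versus 1/7, where the Hurley odds ratios are 3.6 (active) and 4.0 (placebo). The CMH difference is 25.0 points, the midpoint difference 24.7 and the Hurley-averaged difference 23.9, so the midpoint is no further from CMH. The disagreement is in the arm rates. Descriptive statistics by arm will also be shown, and a posterior with an informative prior need not equal the observed proportion.

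Nor can one say that the rates will certainly be low. The cap means that the midpoint never gives Stage III less than its share, but a downward gap also needs Stage III to respond less well. Protocol 4.2 only names Hurley stage among factors theorised to affect adalimumab efficacy.

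Finally, the documents do not show that the prior sits on the wrong quantity. The Hurley mix of the historical studies is not given, and if it was near 50:50 the midpoint is close to right. What stands is that the SAP does not say which mix the 30% describes.

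**Conclusion.** The point holds for the arm rates. As written, the only defined arm rate is a logit midpoint that differs from the stated endpoint whenever Hurley stage matters. The reported rates would be about 2 to 8 points low if Stage III responds less well, the Hurley odds ratio is 2 to 3 and Stage III makes up 20-40%; all three are assumptions. The gap shrinks to about 0 to 2 points at the 50% cap and vanishes without a Hurley effect.

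For a given prior placement the primary difference and the posterior probability of benefit are essentially safe. The harm is to the arm-level posterior rates, to their comparison with the CMH arm rates, and to the meaning of the placebo prior. The change should be made, but the direction of the trial's conclusion is not in doubt on this account.

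**What to change.** 1. State that at each posterior draw each arm's rate is w2·logit⁻¹(b_arm + b_HS2) + w3·logit⁻¹(b_arm - b_HS2), with w2 and w3 the observed Hurley II and III shares in the naive population and the same shares used for both arms. Report the posterior of these rates and of their difference.
2. State which Hurley mix the 30% placebo prior describes, and attach Beta(2.1; 4.9) to the placebo rate at that mix. Centring at this trial's own mix is one option. It presumes that the historical mix was similar, and on the logit scale it only approximates the marginal percentage.

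Item 1 costs a few SAP lines and little code, with no new data. Item 2 can change the difference and P(difference > 0), as step 5 of the working shows, so it has to be settled before the Week 16 database lock and unblinding.
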